## **Accumulation Ratio Analysis**

Part 2:

An ANOVA with a random effect term for subject and fixed effect terms for day will be performed by dose on the loge-transformed PK parameters (AUC(0- $\tau$ ), C $\tau$ , and Cmax). Day will be treated as a class variable in the model. The accumulation ratio of GSK3640254 will be estimated by calculating the ratio of the geometric least squares (GLS) means of PK parameters between Day 14 and Day 1 for Cohort 3,4,5, 6 and expansion, and the corresponding 90% CI for each dose.

*An example of SAS code is included here.*

*ODS output solutionf=stat;*

*Proc Mixed;*

*by dose;*

*class subject day;*

*model logPKpar = day / ddfm=kr;*

*random subject;*

*lsmeans day;*

*estimate 'Day X vs Day 1' day -1 /cl alpha=0.1;*

*run;*

Comparative plots of individual plasma GSK3640254 PK estimates will be generated by dose group [AUC(0- $\tau$ ), C $\tau$ , and Cmax on Day 14 versus AUC(0-24), C24 and Cmax on Day 1] on linear and semi-logarithmic scales. The accumulation ratio will also be listed and summarized along with other PK parameters.

## **Steady State Assessment**

### **Part 2**

Predose concentrations on Day 2 through 14 and C $\tau$  on day 14 from Cohort 3, 4, 5, 6 and expansion of Part 2 of the study will be plotted versus day by treatment (dose). An ANOVA with terms for subject as a random effect and day as a fixed effect will be performed by dose

on the loge-transformed C0 and C $\tau$ . Day will be treated as a continuous variable in the model. Achievement of plasma GSK3640254 steady state will be assessed by visual inspection of plots and calculating the point estimate and 90% CI of the slope of the linear regression of Days 2-14 for Cohort 3, 4, 5,6 and expansion of Part 2 of pre-dose C0 and C $\tau$  versus Day by dose group. To claim that steady state is reached, the pre-dose

concentration slope estimate is close to zero or the 90% CI for the slope estimate includes zero.

*An example of SAS code to assess achievement of steady-state is included here.*

*ODS output solutionf=stat;*

*Proc Mixed;*

*by dose;*

*where (Day in (10,11,12,13,14, 15));*

*class subject;*

*model logCtau = Day/cl alpha=0.1 solution;*

*random intercept/subject=subject type=un;*

*run;*

The same analysis will be repeated with C0 data by dropping one earlier day at time between day 2-14, and the results will be presented in the same table.

### **8.1.5. Food Effect Assessment**

As the study did not administer GSK in fasted conditions, the food effect evaluation can't be performed.

## **9. POPULATION PHARMACOKINETIC (POPPK) ANALYSES**

The population PK analysis and pharmacodynamic analyses will be presented separately from the main clinical study report (CSR).

## 11. APPENDICES

### 11.1. Appendix 1: Protocol Deviation Management and Definitions for PK Parameter Population

A subject meeting any of the following criteria will be excluded from the PK Parameter

Summary Population:

Number	Exclusion Description
01	Failure of any inclusion/exclusion criteria, but subject is still enrolled

## 11.2. Appendix 2: Schedule of Activities

### 11.2.1. Protocol Defined Schedule of Events

#### SAD Cohorts 1 and 2 Screening

Procedure	Screening (up to 28 days before Day 1)
Outpatient Visit	X
Informed Consent	X
Inclusion/Exclusion Criteria and Demography	X
Medical/medication/ drug/alcohol history	X
Full Physical Exam 	X
Columbia Suicide Severity Rating Scale (CSSRS)	X
Height, Weight, BMI	X
Vital signs	X
12 Lead ECG	X
Screening Holter	X
Pregnancy Test	X
Drug/alcohol/cotinine screen	X
HbsAg, HCV, HIV tests	X
Hem/Chem/Urine tests	X

**SAD Cohorts 1 and 2 On-Treatment: Before, During, and After Dosing in Each Period**

Procedure	Periods 1 through 4																				Follow-up (7-14 days post last dosing)	
	Day -2	Day -1	Day 1															Day 2	Day 3	Day 4		Day 5
			Pre- dose	0 h	0.5 h	1 h	1.5 h	2 h	2.5 h	3 h	3.5 h	4 h	4.5 h	5 h	6 h	8 h	12 h	24 h	48 h	72 h		96 h
Admission to Unit	X																					
Outpatient Visit																					X	
Full Physical Exam 		X																X			X	
Weight, BMI		X																				
Vital signs		X			X		X					X		X		X	X	X	X	X	X	
12-lead safety ECGs	X	X	X		X		X				X		X		X	X	X	X	X	X		
Continuous ECG (full time matched baseline on Day-1) 		X	X		X	X	X	X	X	X	X	X	X	X	X	X	X					
Pregnancy Test	X																			X 		
Drug/alcohol/cotinine screen	X																					
Hem/Chem/Urine tests	X																X	X		X		
Single Dosing with GSK3640254 following moderate fat meal				X																		
Plasma PK Sampling 			X		X	X	X	X	X	X	X	X	X	X	X	X	X	X	X	X		
Adverse Event Review	<=====																					
Con Med Review	<=====																					
Furlough from Unit																				X		

HCV=Hepatitis C; BMI= Body mass index; ECG= Electrocardiogram; PK= Pharmacokinetic, SAD=single ascending dose

Note:

1. A Full Physical Exam will include at a minimum, assessments of the Skin, Cardiovascular, Respiratory, Gastrointestinal and Neurological systems.
2. Additional safety ECGs may be printed at the discretion of the PI if prolongation in QT interval is suspected. The frequency of ECGs will support an exploratory endpoint (should clinical development continue) to evaluate the exposure-response relationship between GSK3640254 and QTcF. Once human PK data (e.g. Cmax) are available, the number of ECG time points may be reduced in subsequent dosing groups. At timepoints for ECG extraction, subjects will be supinely resting for at least 10 minutes. When ECG extractions coincide with safety ECGs, vital signs assessment and blood draws, procedures should be carried out in said order.
3. This pregnancy test will be obtained approximately 37 days after the last dose of study treatment
4. The number of PK sampling time points may be reduced in subsequent dosing groups once human PK data are available.

**MAD Cohorts 3, 4, 5 and the Expansion Cohort Screening**

Procedure	Screening (up to 28 days before Day 1)
Outpatient Visit	X
Informed Consent	X
Inclusion/Exclusion Criteria and Demography	X
Medical/medication/ drug/alcohol history	X
Full Physical Exam 	X
CSSRS	X
Height, Weight, BMI	X
Vital signs	X
12 Lead ECG	X
Screening Holter	X
Drug/alcohol/cotinine screen	X
HbsAg, HCV, HIV tests	X
Hem/Chem/Urine tests	X
Pregnancy Test	X

1. A Full Physical Exam will include at a minimum, assessments of the Skin, Cardiovascular, Respiratory, Gastrointestinal and Neurological systems.

**MAD Cohorts 3, 4, 5 and the Expansion Cohort On-Treatment**

Procedure																				Follow-up (7-14 days post last dosing)		
	Day -2	Day -1	Day 1	Day 2	Day 3	Day 4	Day 5	Day 6	Day 7	Day 8	Day 9	Day 10	Day 11	Day 12	Day 13	Day 14	Day 15	Day 16	Day 17		Day 18	
															0h	24h	48h	72h	96h			
Admission to Unit	X																					
Outpatient Visit																					X	
Full Physical Exam 		X						X						X			X			X	X	
CSSRS						X														X		
Weight, BMI		X																				
Vital signs		X	X	X		X		X		X		X		X		X			X		X	
12-lead safety ECGs	X	X	X	X	X	X		X		X		X		X		X	X	X	X	X	X	
Continuous ECG (full time matched baseline on Day-1) 		X	X	X												X	X					
Drug/alcohol/cotinine screen	X																					
Hem/Chem/Urine tests	X			X		X		X		X		X		X		X		X		X	X	
Pregnancy Test	X																				X 	
QD Dosing with GSK3640254 following moderate fat meal			X	X	X	X	X	X	X	X	X	X	X	X	X	X						
Plasma PK Sampling 			X	X	X	X		X		X		X		X		X	X	X	X	X		
Plasma Metabolite Sampling 			X	X												X	X					

Procedure	Day -2	Day -1	Day 1	Day 2	Day 3	Day 4	Day 5	Day 6	Day 7	Day 8	Day 9	Day 10	Day 11	Day 12	Day 13	Day 14	Day 15	Day 16	Day 17	Day 18	Follow-up (7-14 days post last dosing)
															0h	24h	48h	72h	96h		
Urine PK and Metabolite Sampling 			X	X												X	X				
PGx Sampling (if participant consents)	X																				
Adverse Event Review	<=====																				
Con Med Review	<=====																				
Furlough from Unit																				X	

Note:

1. A Full Physical Exam will include at a minimum, assessments of the Skin, Cardiovascular, Respiratory, Gastrointestinal and Neurological systems.
2. ECG data extracted from the Continuous ECG will be assessed before PK sampling, prior to dosing and 0.5,1, 1.5, 2, 2.5, 3, 3.5, 4.5, 5, 5.5, 6, 8, 12 h, and 24 h post dose on Day 1 and Day 14 and on corresponding timepoints on Day -1. At timepoints for ECG extraction, subjects will be supinely resting for at least 10 minutes. When ECG extractions coincide with safety ECGs, vital signs assessment and blood draws, procedures should be carried out in said order. The frequency of EKGs will support an exploratory endpoint to evaluate (should clinical development continue) the ER relationship between GSK3640254 and QTcF. Once human data (eg Cmax) is known, the number of EKG time points may be reduced.
3. This pregnancy test will be obtained approximately 37 days after the last dose of study treatment
4. Plasma PK samples for bioanalysis for GSK3640254 will be collected pre-dose (within 15 minutes prior to dosing) and 0.5,1, 1.5, 2, 2.5, 3, 3.5, 4, 4.5, 5, 5.5, 6, 8, 12 h on Day 1 and Day 14. On dosing days, plasma PK will be collected pre-dose. The number of PK sampling time points may be reduced in the initial MAD cohort as well as further in subsequent MAD dosing groups once human PK data are available in the SAD as well as in the initial MAD cohorts.
5. Plasma Metabolite samples for metabolite identification will be collected pre-dose (within 15 minutes prior to dosing) and at the same time points as for plasma PK samples on Day 1, Day 2 and Day 14, and Day 15. Plasma metabolite samples will not be collected in the expansion cohort.

6. Urine PK and Metabolite Sampling for bioanalysis and metabolite identification will be collected pre-dose (within 1 hour prior to dosing) and from time 0 up to 24 hours on Day 1 and Day 14. Urine samples will not be collected in the expansion cohort.

**11.3. Appendix 3: Assessment Windows**

Not applicable.

## 11.4. Appendix 4: Study Phases and Treatment Emergent Adverse Events

### 11.4.1. Study Phases

Assessments and events will be classified according to the time of occurrence relative to start and/or stop date of the study treatment.

Study Phase	Definition
Pre-Treatment	Date $\leq$ (First) Study Treatment Start Date
On-Treatment	(First) Study Treatment Start Date < Date $\leq$ (Last) Study Treatment Stop Date + 5 days
Post-Treatment	Date > (Last) Study Treatment Stop Date + 5 days

Study epoch of follow-up data for Part 1 will be summarized in following way:

Follow-up from Period 1 will be counted in Period 1 summary;

Follow-up from Period 2 will be counted in Period 2 summary;

Follow-up from Period 3 will be counted in Period 3 summary;

Follow-up from final follow-up will be counted in Period 4 summary.

#### 11.4.1.1. Study Phases for Concomitant Medication

Study Phase	Definition
Prior	If medication end date is not missing and is before 28 days prior to screening visit
Concomitant	Any medication that is not a prior

NOTES:

- Please refer to Appendix 7: Reporting Standards for Missing Data for handling of missing and partial dates for concomitant medication. Use the rules in this table if concomitant medication date is completely missing.

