Sequence 3	Dose 1	Dose 3	Placebo	Dose 7
Sequence 4	Dose 1	Dose 3	Dose 5	Placebo

Cohort 2	Period 1	Period 2	Period 3	Period 4
Sequence 1	Placebo	Dose 4	Dose 6	Dose 8
Sequence 2	Dose 2	Placebo	Dose 6	Dose 8
Sequence 3	Dose 2	Dose 4	Placebo	Dose 8
Sequence 4	Dose 2	Dose 4	Dose 6	Placebo

Part 1 SAD: Sentinel Dosing

To conservatively assess safety, at the start of each dose period of the SAD, 2 out of the 8 participants will serve as sentinel participants with one receiving GSK3640254 and the other receiving placebo. These sentinel participants will be followed clinically for 24 hours after dose administration to monitor for emergence of adverse events. If there are no safety concerns, in the judgment of the PI, on review of the 24-hour safety data (e.g. vital signs, ECGs, and adverse events) for the sentinel participants, the remaining 6 participants will subsequently be administered either GSK3640254 or PBO according to randomization schedules.

Part 1 SAD: Dose Escalation

Dose escalation in Part 1 will be determined by the VH/GSK study team and the PI based on the double-blind (sponsor-unblinded) safety data and the PK data from the current and

previous dose(s). Dose escalation will not exceed approximately 3-fold between doses up to approximately the predicted minimally effective dose and will not exceed 2-fold thereafter. Dose escalation in Part 1 will require (from the current dosing group) at least 24 hours of safety and PK data from 4 participants receiving active drug. Dose escalation will be guided by safety as well as the SAD PK stopping criteria (see Section 8). Due to the alternating dosing periods between Cohort 1 and Cohort 2, a participant in either cohort will receive the next dose after approximately 3 or 4 weeks.

Part 2 (MAD):

Part 2 consists of four ascending repeat-dose cohorts (Cohorts 3 to 6), each with 8 participants (active/PBO=6/2) who will receive a once-daily dose of GSK3640254 or PBO for 14 days. Details of the starting dose and dose escalations in Part 2 (MAD) are provided in Section 5.5.4.

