6.4. Screen Failures

Screen failures are defined as participants who consent to participate in the clinical study but are not subsequently randomized. However, reserve participants only need to undergo the screening process once every 90 days; additionally, reserve participants will still be subject to Day -2 and -1 evaluations in routine fashion (as shown in the **SoA** table). A minimal set of screen failure information is required to ensure transparent reporting of screen failure participants to meet the Consolidated Standards of Reporting Trials (CONSORT) publishing requirements and to respond to queries from regulatory authorities. Minimal information includes demography, screen failure details, eligibility criteria that established screen failure, and any serious adverse events (SAEs).

Individuals who do not meet the criteria for participation in this study (screen failure) may not be rescreened.

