7.7. Concomitant Therapy

Any medication or vaccine (including over-the-counter or prescription medicines, vitamins, and/or herbal supplements) that the participant is receiving at the time of enrollment or receives during the study must be recorded along with:

- reason for use
- dates of administration including start and end dates
- dosage information including dose and frequency

The Medical Monitor should be contacted if there are any questions regarding concomitant or prior therapy.

Participants must abstain from taking prescription or non-prescription drugs (including vitamins and dietary or herbal supplements) within 7 days (or 14 days if the drug is a potential enzyme inducer) or 5 half-lives (whichever is longer) before the start of study treatment until completion of the follow-up visit, unless, in the opinion of the investigator and sponsor, the medication will not interfere with the study or is needed to ensure the participant's safety.

Paracetamol, at doses of ≤ 2 grams/day, is permitted for use at any time during the study.

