**NOTES:**

- If the study treatment stop date is missing, then the AE will be considered to be On-Treatment.
- Time of study treatment dosing and start/stop time of AEs should be considered, if collected.

### 11.4.3. Adverse Events Assignment to Treatment Period for Part 1

Adverse events (AEs) will be assigned to a treatment period and corresponding treatment received in that treatment period after the imputations defined in RAP section 12.7.2 have been performed.

- Treatment Period 1: all AEs with start date/time at the time of or after administration in Treatment Period 1 and before administration in Treatment Period 2
- Treatment Period 2: all AEs with start date/time at the time of or after administration in Treatment Period 2 and before administration in Treatment Period 3
- Treatment Period 3: all AEs with start date/time at the time of or after administration in Treatment Period 3 and before administration in Treatment Period 4
- Treatment Period 4: all AEs with start date/time at the time of or after administration in Treatment Period 4

Thus, AEs occurring during the 1st washout will be assigned to the treatment received in Treatment Period 1, AEs occurring during the 2th washout will be assigned to the treatment received in Treatment Period 2, AEs occurring during the 3rd washout will be assigned to the treatment received in Treatment Period 3 and AEs occurring during final follow-up will be assigned to the treatment received in Treatment Period 4.

### 11.4.4. Concomitant Medication Assignment to Treatment Period for Part 1

Concomitant medications (CMs) will be assigned to a treatment period and corresponding treatment received in that treatment period after the imputations defined in RAP section 12.7.2 have been performed.

- Treatment Period 1: all CMs with start date/time at the time of or after administration in Treatment Period 1 and before administration in Treatment Period 2
- Treatment Period 2: all CMs with start date/time at the time of or after administration in Treatment Period 2 and before administration in Treatment Period 3
- Treatment Period 3: all CMs with start date/time at the time of or after administration in Treatment Period 3 and before administration in Treatment Period 4
- Treatment Period 4: all CMs with start date/time at the time of or after administration in Treatment Period 4

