Thus, CMs occurring during the 1st washout will be assigned to the treatment received in Treatment Period 1, CMs occurring during the 2th washout will be assigned to the treatment received in Treatment Period 2, CMs occurring during the 3rd washout will be assigned to the treatment received in Treatment Period 3, and CMs occurring during follow-up will be assigned to the treatment received in Treatment Period 4.

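### Part 1 concomitant medicines are assigned to periods by start date only, and the prior/concomitant cut-off is tied to screening, not first dose, so some medicines are mislabelled in con-med reporting

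*SAP*

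**What the plan says.** SAP 11.4.1.1 has two classes. A medicine is prior under this condition: "If medication end date is not missing and is before 28 days prior to screening visit". The other class is the remainder: "Any medication that is not a prior". Neither class refers to the date of first dose, although the parent section, 11.4.1, classifies assessments and events relative to the study treatment dates.

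SAP 11.4.4 assigns Part 1 concomitant medicines to a period and to that period's treatment. Period 1 takes "all CMs with start date/time at the time of or after administration in Treatment Period 1 and before administration in Treatment Period 2". Periods 2 and 3 follow the same pattern, and Period 4 has no upper limit. A closing sentence puts washout medicines with the preceding treatment. Stop dates and ongoing status are not used.

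Four other provisions bear on this:

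- **Washout.** Protocol 7.7 sets the pre-dose restriction: "Participants must abstain from taking prescription or non-prescription drugs (including vitamins and dietary or herbal supplements) within 7 days", extended to 14 days for potential inducers or to 5 half-lives if longer. Paracetamol is permitted, and other medicines may be allowed by judgement.
- **Screening.** The schedules allow screening up to 28 days before Day 1. Under Protocol 6.4, "reserve participants only need to undergo the screening process once every 90 days".
- **Dose spacing.** Protocol 5.1 says that "a participant in either cohort will receive the next dose after approximately 3 or 4 weeks".
- **Displays.** SAP 6.2.5 and the notes to SAP Table 1 produce a con-med summary only if there are more than 10 medications. In SAP 11.12.4, Table 1.10 (Part 1) has a total column only. Table 1.21 is the Part 2 counterpart. By-subject listings are Listing 9 (Part 1) and Listing 50 (Part 2).

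**The concern.** The two rules err in opposite directions. The prior/concomitant rule is too wide: a participant who stopped a medicine before dosing, as Protocol 7.7 requires, gets the same label as one who took it during dosing. The Part 1 period rule is too narrow. It repeats the adverse-event bullets of SAP 11.4.3, where onset date is a natural anchor, but a medicine is an exposure with a duration. For adverse events, SAP 11.4.2 at least counts one that worsens in a later period in both periods. Medicines have no such provision.

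What is at stake is the label a reader uses when asking whether a co-medication was present at a given dose, for example beside a laboratory change or an unusual concentration profile. With six active participants per Part 1 dose, such questions are settled participant by participant. In a four-period crossover, the wrong period also means the wrong treatment, possibly placebo.

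**Working it through.** The plan states no figure to reproduce, so the check applies its rules to dates. Let time 0 be first dose.

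**Cut-off.** Prior requires end date < screening date − 28. The earliest end date still called concomitant is therefore screening date − 28.

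| Screening relative to first dose | Source | Earliest end date still concomitant |
|---|---|---|
| −28 | Schedules of activities | −28 − 28 = −56 |
| −30 | Protocol 5.1, which gives a 30-day window | −30 − 28 = −58 |
| −90 | Protocol 6.4, reserve participants | −90 − 28 = −118 |

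With screening at −28, medicines that ended at −50, −20 or −8 are all concomitant, and one that ended at −57 is prior. The one ending at −8 already meets a 7-day washout. All the pre-dose cases labelled concomitant also match none of the four Part 1 period bullets, so 11.4.1.1 creates concomitant records that 11.4.4 cannot place.

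**Period assignment.** Doses 3 weeks apart fall on days 0, 21, 42 and 63; doses 4 weeks apart fall on days 0, 28, 56 and 84. The overlap rule assigns a medicine to a period if it starts before that period ends and it ends on or after that period's dose or is ongoing. Results are the same for both spacings.

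| Medicine | SAP 11.4.4 | Overlap rule |
|---|---|---|
| Day 15 to day 30 | Period 1 | Periods 1 and 2 |
| Day 15, ongoing | Period 1 | Periods 1 to 4 |
| Day −5, ongoing | none | Periods 1 to 4 |

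In the first row the medicine is in use at the Period 2 dose (day 21 or 28) but is credited only to the Period 1 treatment. In the second it is missing from three of four periods, and in the third from all four.

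**Partial dates.** SAP 11.7.2.1 imputes partial con-med start dates to day 01 and month Jan, with no floor at first dose, and 11.4.4 is applied after imputation. An on-study start can thus be moved before Period 1 and lose its period.

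**Where the labels are used.** Table 1.10 has no treatment columns, so period assignment cannot change a count in it. SAP 11.4.4 covers Part 1 only, so Table 1.21 is not affected by it. The cut-off decides who counts as concomitant in both tables. No PK, dose-proportionality or safety analysis in the SAP uses either label.

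**The case against.** The strongest reply is that little depends on these labels. Table 1.10 is total-only, the summaries are conditional on more than 10 medications, and no model or endpoint uses them. Part 1 plans about 16 participants. By-subject listings are planned, start and end dates are recorded under Protocol 7.7, and a reader can check overlap by hand. All of this stands, and it caps the importance of the point.

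The extremes of 56 and 118 days are also unlikely to be typical. Protocol 7.7 requires recording of medicines taken at enrolment or during the study, so one that ended before screening may never be recorded, although the medication history at screening may capture some. Medicines stopped between screening and dosing are within reach of the recording requirement. Three of four periods missed needs one continuous record across about 9 to 12 weeks.

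The wide look-back also has a use. It never drops a medicine taken during exposure, and it keeps visible the pre-dose medicines needed to check the washout. SAP 11.12.4 groups its tables under a heading that mentions prior medications, but no display is titled for them. Moving the cut-off alone could therefore remove these medicines from view. That objection is sound, and the fix has to meet it.

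None of this makes the labels right. The start-date rule gives a definite wrong answer for a continuing medicine and no answer for one begun before Period 1.

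**Conclusion.** The point holds as a minor reporting matter. In Part 1, a medicine continuing through a later dose is attributed only to the earlier treatment, and one begun before Period 1 and ongoing is attributed to none. This affects the dataset variable and any listing that shows it. In both parts, recorded medicines stopped before first dose can be counted as concomitant, which can inflate Tables 1.10 and 1.21 if those tables are produced. How many medicines are affected cannot be told from the documents. The day limits assume the full screening windows and that such medicines are recorded.

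A reader might infer that the summary tables misreport co-medication by treatment, or that evidence for a drug-free background, and with it the PK and safety results, is undermined. The documents do not support either reading. Table 1.10 carries no treatment columns. The background rests also on exclusion criterion 9, Protocol 7.7, deviation tracking and the listings. No planned PK, safety or endpoint analysis depends on these labels.

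**What to change.** - **SAP 11.4.4.** Assign each medicine to every Part 1 period that its use overlaps: start before the period ends, and end on or after that period's dose or ongoing. Include medicines started before Period 1.
- **SAP 11.4.1.1.** Define concomitant as any use on or after first dose of study treatment, including a missing or ongoing end date, and prior as ended before first dose.
- **Listings 9 and 50.** Keep prior medicines in these by-subject listings, flagged as prior, so that compliance with the Protocol 7.7 washout can still be checked.

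The cost is a few SAP sentences, a date comparison in programming and a prior/concomitant flag in two listings. No new data are needed. One medicine may appear under several Part 1 periods, which is accurate, although an imputed early start date would then also count as overlap from Period 1 onward.
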